9.2 Pooling of Centers

In order to provide overall estimates of the treatment effect, data will be pooled across centers. The factor center will not be considered in statistical models.

9.3 Presentation and Definition of General Considerations

9.3.1 Presentation of Continuous and Qualitative Variables

Continuous variables will be summarized using descriptive statistics, i.e.

- number of subjects (N), number of subjects with non-missing values
- mean, standard deviation (SD)
- median, 25th Percentile - 75th Percentile (Q1-Q3)

- minimum (Min) and maximum (Max)

Qualitative variables will be summarized by counts and percentages.

Unless otherwise stated the calculation of proportions will be based on the number of subjects of the analysis set of interest. Therefore, counts of missing observations will be included in the denominator and presented as a separate category.

9.3.2 Definition of Baseline

The last non-missing measurement (scheduled or unscheduled) prior to the first trial drug administration will be used as the baseline measurement. Definition of baseline value will be used as baseline for all safety and efficacy analysis. If an assessment is planned to be performed on Week 1 Day 1 and the assessment is performed on the same day as the first dose of study treatment, it will be assumed that it was performed prior to study treatment administration if assessment time point is not collected or is missing. If assessment time points are collected, the observed time point will be used to determine pre-dose on study day 1 for baseline calculation. Unscheduled assessments will be used in the determination of baseline. However, if time is missing, an unscheduled assessment on study day 1 will be considered to have been obtained after study treatment administration.

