ECOG PS 	X	X 	X	X	X	X	X	X	2-weekly	X	X		
Enrolment (if eligible) 	X												
DLT assessment 		X	X 										
12-lead ECG	X	X	X	X	As indicated and decided by Investigator					X			
Hematology and hemostaseology	X		X	X	X	X	X	X	2-weekly	X	X		
Core serum chemistry 			X	X		X	X		2-weekly		X		
Full serum chemistry 	X				X			X	6-weekly	X			

Assessment	Clinical Screening / Baseline Assessments	Treatment Phase 								EOT Visit 	Safety Follow-up 	Long-term Follow-up 	
		≤ Day -14 to Day -1	V1	V2	V3	V4	V5	V6	V7				Until progression
			W1	W3	W5	W7	W9	W11	W13				
			D1	D15	D29	D43	D57	D71	D85				
Full urinalysis 	X									X			
Basic urinalysis 				X			X	6-weekly					
Serum beta-hCG pregnancy test (if applicable) 	X												
Urine pregnancy test (if applicable) 		X		X		X		X	4-weekly	X			
CCI													
Premedication 		X	X	X	X								
Avelumab administration		X	X	X	X	X	X	X	2-weekly				
Concomitant medication and procedures 	Collected at each study visit through the 30-day Safety Follow-up Visit												

Assessment	Clinical Screening / Baseline Assessments	Treatment Phase 								EOT Visit 	Safety Follow-up 	Long-term Follow-up 		
		≤ Day -14 to Day -1	V1	V2	V3	V4	V5	V6	V7	Until progression	Within 7 days after decision to discontinue IMP 	30 days (± 5 days) after last IMP	Phone Call 90 days (± 5 days) after last IMP	Every 12 weeks (± 7 days) 
			W1	W3	W5	W7	W9	W11	W13					
			D1	D15	D29	D43	D57	D71	D85					
AE collection 	AEs are collected through the 30-day Safety Follow-up Visit Treatment-related nonserious AEs are collected until the 90-day Safety Follow-up Phone Call													
SAE collection 	All SAEs are documented until the 90-day Safety Follow-up Phone Call Ongoing SAEs at the 30-day Safety Follow-up Visit will be followed up													
Free T4 and TSH	X				X			X	6-weekly	X	X			
PK sampling 	See Table 1-3													
ADA sampling 	See Table 1-3													
Survival 		X	X	X	X	X	X	X	Every visit	X	X	X	X	
Further anticancer therapy 											X	X	X	

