#### 7.4.4 Vital Signs, Physical Examinations, and Other Assessments

The ECOG performance status (see Section 12, Appendix IV) will be assessed at Clinical Screening and at subsequent visits as indicated in the Schedule of Assessments (Table 1-1 and Table 1-2) and documented in the eCRF, even if the IMP is on hold for the subject. More frequent examination may be performed at the Investigator's discretion, if medically indicated.

Body weight (to the nearest 0.1 kilogram [kg]) will be measured at Clinical Screening and at subsequent visits as indicated in the Schedule of Assessments (Table 1-1 and Table 1-2) and

documented in the eCRF. Body height in centimeters (cm) will be measured at Clinical Screening only.

Physical examination will include an examination of general appearance, skin, neck (including thyroid), eyes, ears, nose, throat, lungs, heart, abdomen, back, lymph nodes, extremities, and a basic nervous system evaluation. A full physical examination will be conducted at Clinical Screening, at the EOT Visit, and at the 30-day Safety Follow-up Visit. At visits during the Treatment Phase (see Schedule of Assessments [Table 1-1 and Table 1-2]), the physical examination will be symptom-directed. Results from the physical examination, including any abnormalities, will be documented in the eCRF. Abnormal findings are to be reassessed at subsequent visits. Details of the physical examination must be present in the source documentation at the study site.

A 12-lead ECG will be performed and recorded at Clinical Screening and as indicated in the Schedule of Assessments (Table 1-1 and Table 1-2). All subjects will have ECG assessment at baseline, and at the first 3 times of study drug treatment after avelumab infusion. In following visits, ECG will be arranged if considered necessary by the Investigator. Electrocardiograms will be performed in the supine position after the subject has been breathing quietly for 5 minutes. The ECG results will be used to evaluate heart rate, atrial-ventricular conduction, QR\* and QT intervals, and possible arrhythmias. Interpretation of the ECG trace must be made by a qualified physician and documented on the ECG eCRF. Each ECG trace should be labeled with the Study Number, Subject Identifier Number, and date, and kept in the source documents at the site.

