15.5 Other Safety or Tolerability Evaluations

15.5.1 ECG

A shift table from baseline to the worst on-treatment conclusion will be tabulated with the subsequent categories:

- Normal ECG
- Abnormal ECG
 - ECG abnormalities non-clinically significant
 - ECG abnormalities clinically significant
- Missing
- Overall

Conclusions are sorted as Normal/Abnormal non-clinically significant/Abnormal clinically significant, the latest one being considered as the worst. If no post-baseline data are available the worst on-treatment result will be accounted as missing. If significance is not provided, the conclusion will be classified as “Abnormal ECG”. This “Abnormal ECG” category will count abnormal conclusion with missing significance only.

Quantitative data will also be examined for trends using descriptive statistics (n, missing, mean, SD, median, Q1, Q3, minimum, and maximum) of actual values and absolute changes from baseline to each visit.

A listing of ECG values will be provided with all information included from the ECG where the abnormality was observed.

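### A Day 1 ECG with no recorded time becomes the baseline under SAP 9.3.2, although the protocol schedules that ECG after the infusion

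*SAP*

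**What the plan says.** Protocol 7.4.4 separates a baseline ECG from three post-infusion ECGs: "All subjects will have ECG assessment at baseline, and at the first 3 times of study drug treatment after avelumab infusion". The ECG rows of Tables 1-1 and 1-2 agree. Each fixes an ECG at Screening, V1 (Day 1), V2 and V3, and then switches to "As indicated and decided by Investigator". Table 1-1 adds one at the EOT Visit, and a footnote to Table 1-2 applies the same EOT procedures to the once-weekly cohort. Protocol 7.2 and 7.2.4 place baseline measurements, including the 12-lead ECG, in Clinical Screening. No pre-dose ECG is scheduled on Day 1.

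SAP 9.3.2 sets the general rule: "The last non-missing measurement (scheduled or unscheduled) prior to the first trial drug administration will be used as the baseline measurement". For a planned Week 1 Day 1 assessment done on the first dosing day, it adds that "it will be assumed that it was performed prior to study treatment administration if assessment time point is not collected or is missing". Where a time exists, "If assessment time points are collected, the observed time point will be used to determine pre-dose on study day 1 for baseline calculation". The opposite default, under which an untimed Day 1 assessment counts as post-dose, covers unscheduled assessments only. The definition applies to every safety and efficacy analysis.

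SAP 15.5.1 uses baseline twice for ECG: "A shift table from baseline to the worst on-treatment conclusion will be tabulated", and quantitative values are summarised as change from baseline by visit. It has no baseline rule of its own.

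**The concern.** The SAP default suits assessments normally done before dosing. The planned Day 1 ECG is the reverse case, since the protocol states that it follows the infusion. For this assessment the default therefore presumes the opposite of the scheduled timing, and nothing elsewhere in the SAP corrects it.

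At stake is the ECG part of the safety description. The baseline of the shift table and of the change summaries could contain the response to the first dose, and a first-infusion abnormality could be tabulated as pre-existing. Safety and tolerability in Chinese subjects are a secondary objective, and Protocol 3.3 says that the study will support a marketing submission in China. With so few subjects, a handful of misclassified ECGs would be visible in the tables.

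**Working it through.** The plan states no figure to reproduce. The check applies SAP 9.3.2 to the ECG schedule.

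**Step 1: which ECG becomes baseline.** Take a subject with ECGs at Screening and at V1, the latter done on the first dosing day as planned.

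| V1 ECG time | SAP 9.3.2 classes V1 as | Baseline | Scheduled post-infusion ECGs left on treatment |
|---|---|---|---|
| Recorded, after infusion | Post-dose | Screening (correct) | V1, V2, V3 = 3 |
| Missing or not collected | Pre-dose | V1 (post-infusion) | V2, V3 = 2 |

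In the second row V1 is later than Screening, so as the last value classed as pre-dose it wins. A subject who stops after one dose and has no later ECG would have the worst on-treatment result counted as missing under SAP 15.5.1, despite having a post-infusion trace.

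**Step 2: shift table for an affected subject.**

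| Screening / V1 / later worst | Correct shift | Shift under the rule |
|---|---|---|
| Normal / abnormal / abnormal | Normal to abnormal | Abnormal to abnormal |
| Normal / abnormal / normal | Normal to abnormal | Abnormal to normal |
| Abnormal / normal / abnormal | Abnormal to abnormal | Normal to abnormal |

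The first two rows lose a new abnormality. The third creates one.

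**Step 3: change from baseline.** Let d = (V1 value) − (Screening value). At a later visit v:

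- correct change = Y(v) − Y(Screening)
- change under the rule = Y(v) − Y(V1) = correct change − d

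The same error, −d, enters every later visit. Assumed values for illustration only: Screening 400 and V1 410, so d = 10.

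- Later value 410: correct change +10, under the rule 0 (toward no change).
- Later value 400: correct change 0, under the rule −10 (a spurious change).

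If k of n subjects are affected, the mean change at a later visit is wrong by −(k/n) × (mean d among those affected). In a cohort of 6 with d = 10, that is 0 for k = 0, −10/6 = −1.7 for k = 1, −5 for k = 3 and −10 for k = 6.

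**Step 4: how many subjects.** Planned enrolment is 3 or 6 (3 mg/kg) + 6 (10 mg/kg every 2 weeks) + 6 (20 mg/kg) + 6 (10 mg/kg once weekly) = 21 or 24, matching the synopsis. If the eCRF always captures ECG time, 0 are affected. If it has no time field, every subject with a Day 1 ECG is. If the field exists but is sometimes blank, the number lies between.

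**The case against.** The strongest reply is that the trigger is unproven. SAP 9.3.2 honours a recorded time, so nothing goes wrong if ECG times are collected and complete. A reader might infer that they are not collected from "Each ECG trace should be labeled with the Study Number, Subject Identifier Number, and date, and kept in the source documents at the site", which names a date and no clock time. That inference fails: the sentence concerns the label on the trace kept at the site, while the ECG eCRF page is a separate item whose fields the documents do not show. All 21 to 24 subjects is therefore a ceiling and not an estimate. This part of the reply stands. It limits the size of the problem but does not make the rule right when a time is absent.

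A second reply concerns direction. A reader might infer that a post-dose baseline always pulls results toward no change. Steps 2 and 3 show that it need not: an effect confined to the first infusion produces spurious later changes, and the untied EOT ECG is an obvious place for that to appear.

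Third, an acute effect is not wholly hidden. The ECGs after infusions 2 and 3 remain on treatment, SAP 15.5.1 also summarises actual values and lists abnormal ECGs, and findings that meet the protocol's criteria for an adverse event are reported whatever the baseline flag. This softens the consequence but leaves the two baseline-dependent outputs wrong for affected subjects.

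Finally, the protocol makes the intended baseline clear enough that a programmer might choose Screening unprompted. But SAP 9.3.2 gives an explicit instruction to the contrary, with no ECG exception.

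**Conclusion.** The point holds as a wrong default in the SAP. For the planned Day 1 ECG, the presumption of pre-dose timing contradicts Protocol 7.4.4, and whenever the time is missing or not collected it puts a post-infusion ECG in place of the screening ECG. Between 0 and about 21 to 24 subjects are affected, and the documents cannot narrow that range.

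The conclusion assumes that the Day 1 ECG is done after the infusion as scheduled and that a screening ECG exists. It does not support a claim that ECG times are uncollected, that every subject has a contaminated baseline, or that the bias runs in one direction. The affected outputs are descriptive safety tables. The DLT and PK primary endpoints are not touched. It is a modest defect, worth correcting because the correction is nearly free.

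**What to change.** Add to SAP 9.3.2:

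> For ECG, the pre-dose assumption does not apply: a Day 1 ECG without a recorded time is treated as post-dose, and baseline is the last ECG (scheduled or unscheduled) before first dose, normally the screening ECG. A recorded time, where available, determines pre- or post-dose status.

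This extends to the planned ECG the default that the SAP already uses for untimed unscheduled Day 1 assessments. A flat rule that the Day 1 ECG is post-dose whatever time was recorded should be avoided. It would override a genuine pre-dose time, which the SAP rightly honours, and could leave a subject whose only pre-dose ECG was taken on Day 1 without a baseline.

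The cost is one short SAP addition and a matching line in the dataset specification, with no new data. If ECG times turn out to be complete, the addition changes no result. It is also worth checking whether the ECG eCRF page has a time field, since that settles how many subjects are concerned.

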9.3.3 Definition of Duration

Duration will be calculated by the difference of start and stop date + 1, unless otherwise specified.

9.3.4 Conversion Factors

The following conversion factors will be used to convert days into weeks or months or years, or vice versa:

- 1 week = 7 days
- 1 month = 30.4375 days
- 1 year = 365.25 days

9.3.5 Handling of Missing Data

Unless otherwise specified (Section 11, 13, 14 and 15), missing data will not be imputed.

In all subject data listing imputed values will be presented. In all listings imputed information will be flagged. Partial dates, which are not to be imputed according to this IAP, will be presented in the format like “____YYYY”. In case imputation is defined, imputed date with flag (i.e., D for day, M for month) will be reported.

Missing statistics, e.g. when they cannot be calculated, should be presented as “NA”. For example, if n=1, the measure of variability (SD) cannot be computed and should be presented as “NA”.

9.3.6 Presentation of PK Concentration Data

Individual PK concentrations will be reported with the same precision as the source data provided by the bioanalytical laboratory or clinical laboratory regardless of how many significant figures or decimal places the data carry. Actual elapsed sample collection times will be rounded to 2 decimal places for reporting purposes only, in by-subject listings.

Pharmacokinetic concentration data will be descriptively summarized using: number of non-missing observations (n), arithmetic mean (Mean), standard deviation (SD), coefficient of variation (CV%), minimum (Min), median (Median), and maximum (Max).

Descriptive statistics of PK concentration data will be calculated using values with the same precision as the source data, and rounded for reporting purposes only. The following conventions will be applied when reporting descriptive statistics of PK concentration data:

- Mean, Min, Median, Max: 3 significant digits
- SD: 4 significant digits
- CV%: 1 decimal place

Values below the lower limit of quantification (LLOQ) will be taken as zero in the calculation of descriptive statistics for avelumab serum concentrations.

9.3.7 Presentation of PK Parameter Data

Pharmacokinetic parameter data will be descriptively summarized using: number of non-missing observations (n), number of missing observations (n), Mean, SD, CV%, standard error of the mean (SEM), Min, Median, Max, geometric mean (GeoMean), the geometric coefficient of variation (GeoCV%), and the 95% confidence interval (CI) for the GeoMean (LCI 95% GM, UCI 95% GM).

Pharmacokinetic parameter C_{max} will be reported with the same precision as the source data and t_{max} will be reported to two decimal places. All other PK parameters will be reported to 3 significant figures. In export datasets, as well as in the Study Data Tabulation Model (SDTM) PP/XD domain, PK parameters will be provided with full precision, and will not be rounded. Descriptive statistics of PK parameter data will be calculated using full precision values, and rounded for reporting purposes only.

The following conventions will be applied when reporting descriptive statistics of PK parameter data:

- Mean, Min, Median, Max, GeoMean, 95% CI: 3 significant digits

- SD, SEM: 4 significant digits
- CV%, GeoCV%: 1 decimal place

9.3.8 Software

All statistical analyses will be performed using SAS® software version 9.4.

Pharmacokinetic parameters will be derived using noncompartmental methods with the validated computer program Phoenix® WinNonlin® 6.4 or higher (Certara, L.P., Princeton, New Jersey, USA). Pharmacokinetic figures will be developed using SigmaPlot® 12.5 or higher (Systat Software, Inc, San Jose, California, USA), Phoenix® WinNonlin® 6.4 or higher, or SAS® Windows Version 9.4 or higher (Statistical Analysis System, SAS-Institute, Cary, North Carolina, USA).

10 Trial Subjects

The subsections in this section include specifications for reporting subject disposition and treatment/trial discontinuations. Additionally, procedures for reporting protocol deviations are provided.

10.1 Disposition of Subjects and Discontinuations

Descriptive statistics will be used to summarize subject disposition and reason for discontinuation by dose level/cohort and in overall, based on the electronic case report form (eCRF) data.

- Number of subjects screened
- Number of subjects who discontinued before treatment overall and by the main reason
- Number of subjects who discontinued from the trial after randomization, grouped by the primary reason
- Number of subjects who discontinued from the trial treatment by the primary reason (e.g. subject did not meet all eligibility criteria, adverse event, lost to follow-up, protocol non-compliance, death, progressive disease, withdrew consent from avelumab, other)
- Number of subjects who received at least 1 dose of trial treatment
- Number of subjects still on treatment
- Number of subjects re-initiated the trial treatment

10.2 Protocol Deviations

10.2.1 Important Protocol Deviations

The following summary tables and listings of important protocol deviations will be provided in Screening analysis set (separately for the inclusion/exclusion criteria or post inclusion deviations):

- Frequency table per reason of important protocol deviations
- Listing of important protocol deviations

11 Demographics and Other Baseline Characteristics

Analysis sets: Safety analysis set

11.1 Demographics

Demographic characteristics will be summarized by dose level/cohort and overall as follows:

- Sex: Male, Female.
- Race: Asian, Other.
- Ethnicity: Chinese, Other.
- Age (years): descriptive statistics.
- Age categories: < 65 years, \geq 65 years (further break-down: 65 - < 75 years, 75 - < 85 years, \geq 85 years).

Specifications for computation:

- Age (years): (date of given informed consent – date of birth + 1) / 365.25. The integer part of the calculated age will be used for reporting purpose.
 - In case of missing day for at least one date, but month and year available for both dates:
For the derivation of age, the day of informed consent and the day of birth will be set to 1 and the formula above will be used.
 - In case of missing month for at least one date, but year available for both dates:
For the derivation of age, the day and the month of informed consent and the day and month of birth will be set to 1 and the formula above will be used.
- BMI (kg/m²) = weight(kg)/[height(m)]²

A supportive demographic listing will be provided.

11.2 Medical History

The summary tables by dose level/cohort and overall for Medical History will also be provided detailing the number and percentage of subjects by Medical Dictionary for Regulatory Activities (MedDRA) in terms of primary System Organ Class (SOC) (ordered alphabetically) and Preferred Term (PT) (ordered alphabetically); each subject will be counted only once within each PT or SOC (eCRF” MEDICAL HISTORY”).

Medical history will be displayed in terms of primary SOC and PT in alphabetical order and also listed.

11.3 Other Baseline Characteristics

Information of other baseline characteristics collected at the baseline evaluation visit will be summarized in total and by dose level/cohort. Summary statistics will be presented for:

- Serology: Hepatitis B, hepatitis C, and HIV tests
- Nicotine use status: Never, Regular, Occasional, Former
- Nicotine Consumption: summary statistics
- Alcohol use status: Never, Regular, Occasional, Former
- ECOG performance status
 - 0: Fully active, able to carry on all pre-disease performance without restriction.
 - 1: Restricted in physically strenuous activity but ambulatory and able to carry out work of a light or sedentary nature, e.g., light house work, office work.
 - 2: Ambulatory and capable of all self-care but unable to carry out any work activities. Up and about more than 50% of waking hours.
 - 3: Capable of only limited self-care, confined to bed or chair more than 50% of waking hours.
 - 4: Completely disabled. Cannot carry on any self-care. Totally confined to bed or chair.
 - 5: Dead.

Baseline characteristics with respect to vital signs, physical examinations, and hematology/biochemistry will be part of Section 15.

Disease history

Disease history is collected in “DISEASE HISTORY” pages.

Summary statistics for the following parameters will be presented by treatment dose

- Site of primary tumor

- Metastatic sites
- Time since initial diagnosis (months)
- Time since documented, locally advanced, inoperable or metastatic disease (months)
- TNM classification at initial diagnosis: each T, N, M category will be described (TX, T0, N1, etc.)
- TNM classification at study entry

Specifications for computation:

- Time since initial cancer diagnosis (months) = (date of first avelumab administration – date of initial cancer diagnosis)/30.4375
- Time since documented, locally advanced, inoperable or metastatic disease (months) = (date of first avelumab administration – date of documented, locally advanced, inoperable or metastatic disease)/30.4375
- Time since progression disease (months) = (date of first administration – date of progression disease) / 30.4375

Incomplete dates for disease history (initial diagnosis date, date of documented, locally advanced, inoperable or metastatic disease diagnosis, date of response or progression in prior treatment) will be imputed as follows:

- If the day is missing, it will be imputed to the 15th day of the month.
- If both day and month are missing and the year is prior to the year of the first study treatment, the month and day will be imputed as July 1st.
- If both day and month are missing and the year is same as the year of the first study treatment, the month and day will be imputed as January 1st.
- If the date is completely missing, no imputation will be performed.

Listing of disease history will be provided with all relevant data (primary site of tumor, sub-site, initial diagnosis date, first occurrence of locally advanced, inoperable or metastatic disease, histopathological classification, metastasis site, TNM classification, etc.) and derived variables used in the above table.

12 Previous or Concomitant Medications/Procedures

